9.4.1.4 Management of Hypertension

Hypertension is a recognized side-effect of treatment with drugs inhibiting vascular endothelial growth factor (VEGF) signaling. Investigators should therefore ensure that subjects enrolled to receive treatment with lenvatinib have BP $<$ 95th percentile [BP \leq 150/90 mm Hg] for sex, age, and height/length at the time of study entry and, if known to be hypertensive, have been on a stable dose of antihypertensive therapy for at least 1 week before Cycle 1 Day 1. Early detection and effective management of hypertension are important to minimize the need for lenvatinib dose interruptions and reductions. Antihypertensive agents should be started as soon as elevated BP (systolic BP \geq 95th percentile [BP \geq 140 mm Hg] or diastolic BP \geq 95th percentile [BP \geq 90 mm Hg]) is confirmed on 2 assessments obtained 1 hour apart. One BP assessment is defined as the mean value of 3 measurements obtained at least 5 minutes apart. The choice of antihypertensive treatment should be individualized to the subject's clinical circumstances and follow standard medical practice. For previously normotensive subjects, monotherapy with one of the classes of antihypertensives should be started when systolic BP \geq 95th percentile [BP \geq 140 mm Hg] or diastolic BP \geq 95th percentile [BP \geq 90 mm Hg] is first observed on 2 assessments obtained 1 hour apart. For those subjects already on antihypertensive medication, the dose of the current agent may be increased, if appropriate, or 1 or more agents of a different class of antihypertensive should be added. For subjects with hypertension and proteinuria, treatment with an angiotensin-converting enzyme (ACE) inhibitor or angiotensin-II receptor antagonist is preferred.

Lenvatinib should be withheld in any instances where a subject is at imminent risk to develop a hypertensive crisis or has significant risk factors for severe complications of uncontrolled hypertension (eg, BP \geq 99th percentile [BP \geq 160/100 mm Hg], significant risk factors for cardiac disease, intracerebral hemorrhage, or other significant comorbidities). Once the subject has been on the same antihypertensive medications for at least 48 hours and the BP is controlled, lenvatinib should be resumed as described below.

During the Treatment Period, subjects with systolic BP \geq 99th percentile [BP \geq 160 mm Hg] or diastolic BP \geq 99th percentile [BP \geq 100 mm Hg] must have their BP monitored every 2 weeks (on Day 15 or more frequently as clinically indicated) until systolic BP has been $<$ 95th percentile [\leq 150 mm Hg] and diastolic BP has been $<$ 95th percentile [\leq 95 mm Hg] for 3 consecutive months. If a new event of systolic BP \geq 99th percentile [BP \geq 160 mm Hg] or diastolic BP \geq 99th percentile [BP \geq 100 mm Hg] occurs, the subject must resume the Day 15 evaluation until systolic BP has been $<$ 95th percentile [\leq 150 mm Hg] and diastolic BP has been $<$ 95th percentile [\leq 95 mm Hg] for 3 consecutive months.

The following guidelines should be followed for the management of systolic BP \geq 99th percentile [BP \geq 160 mm Hg] or diastolic BP \geq 99th percentile [BP \geq 100 mm Hg] confirmed on repeat measurements after an hour:

- Continue lenvatinib and institute antihypertensive therapy for subjects not already receiving antihypertensive medication.
- For those subjects already on antihypertensive medication, the dose of the current agent may be increased, if appropriate, or 1 or more agents of a different class of antihypertensive should be added.
- If systolic BP \geq 99th percentile [BP \geq 160 mm Hg] or diastolic BP \geq 99th percentile [BP \geq 100 mm Hg] persists despite maximal antihypertensive therapy, then lenvatinib administration should be interrupted and restarted at a lower dose QD (one dose level reduction [20%] as specified in [Table 2](#)) only when systolic BP $<$ 95th percentile [BP \leq 150 mm Hg] and diastolic BP $<$ 95th percentile [BP \leq 95 mm Hg] and the subject has been on a stable dose of antihypertensive medication for at least 48 hours.
 - If systolic BP \geq 99th percentile [BP \geq 160 mm Hg] or diastolic BP \geq 99th percentile [BP \geq 100 mm Hg] recurs despite optimal management of hypertension with antihypertensive medications (either by dose increase or the addition of a different class of antihypertensive), then lenvatinib administration should be interrupted and restarted at a lower dose QD (one dose level reduction [20%] as specified in the table above) only when systolic BP $<$ 95th percentile [BP \leq 150 mm Hg] and diastolic BP $<$ 95th percentile [BP \leq 95 mm Hg] and the subject has been on a stable dose of antihypertensive medication for at least 48 hours.
 - If systolic BP \geq 99th percentile [BP \geq 160 mm Hg] or diastolic BP \geq 99th percentile [BP \geq 100 mm Hg] recurs despite optimal management of hypertension with antihypertensive medications (either by dose increase or the addition of a different class of antihypertensive), then lenvatinib administration should be interrupted and a restart of lenvatinib should be discussed with the sponsor.

The following guidelines should be followed for the management of Grade 4 hypertension (life-threatening consequences):

- Institute appropriate medical management
- Discontinue lenvatinib

Figure 2 shows the procedures associated with the management of hypertension.

[figure not shown]

Figure 2 Management of Hypertension

BP = blood pressure, HTN = hypertension, Tx = treatment.

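### For a previously untreated subject with confirmed BP at or above the 99th percentile (160/100 mm Hg at ages 18 to 25), Protocol Section 9.4.1.4 supports both withholding and continuing lenvatinib, with no stated precedence

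*Protocol*

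**What the plan says.** Protocol Section 9.4.1.4 contains two instructions that meet at the same blood pressure level.

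- **Withhold.** "Lenvatinib should be withheld in any instances where a subject is at imminent risk to develop a hypertensive crisis", or has important risk factors for serious complications of uncontrolled hypertension. The examples in the parenthesis begin "eg, BP \geq 99th percentile [BP \geq 160/100 mm Hg], significant risk factors for cardiac disease". The paragraph then covers resumption: "Once the subject has been on the same antihypertensive medications for at least 48 hours and the BP is controlled, lenvatinib should be resumed", and refers to what is described below it.
- **Continue.** After a paragraph on monitoring frequency, a set of guidelines begins "The following guidelines should be followed for the management of systolic BP \geq 99th percentile [BP \geq 160 mm Hg" or diastolic BP at or above the 99th percentile [100 mm Hg], confirmed on repeat measurement after an hour. The first bullet is "Continue lenvatinib and institute antihypertensive therapy for subjects not already receiving antihypertensive medication". For subjects already on antihypertensives, the second bullet adjusts that treatment and does not mention lenvatinib. Interruption appears in the third bullet, when BP at that level "persists despite maximal antihypertensive therapy, then lenvatinib administration should be interrupted and restarted at a lower dose QD", and again on recurrence.

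The synopsis, under Management of Hypertension, repeats both texts with the same thresholds.

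**The concern.** A protocol instruction on holding study drug should lead every site from the same reading to the same action. Here the level offered as an example of when to withhold is also the level that opens a pathway whose first step is to continue.

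Two things are at stake. The first is the safety of the children and young adults being treated. The second is the dose-modification data: whether a subject has a zero-dose period, and at what dose treatment resumes, decides how SAP Section 5.6.1.3 classifies the episode. Site-to-site differences in reading the protocol would then appear in those tables as differences in tolerability.

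**Working it through.** There is no figure to recompute. The check places the two texts side by side and follows one subject through them.

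**1. Do the thresholds coincide?**

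| | Withhold text | Continue text |
|---|---|---|
| Percentile | at or above 99th | systolic or diastolic at or above 99th |
| Ages 18 to 25 | at or above 160/100 mm Hg | systolic at or above 160, or diastolic at or above 100 |
| Confirmation | none stated | repeat after an hour |
| Subjects named | at imminent risk of crisis, or with important risk factors | not already on antihypertensives |
| Lenvatinib | withhold | continue |

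The percentile threshold is identical. The slash in 160/100 does not say whether both values are needed, but a subject with both meets either text. A confirmed reading satisfies the continue text and also matches the withhold text's example.

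**2. Who is explicitly caught?** A subject not on antihypertensives with a confirmed reading at this level. One paragraph supports holding the drug; the other says to go on with it. For a subject already treated, continuation has to be inferred from the fact that interruption is reserved for persistence or recurrence.

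**3. Is precedence stated?** No visible sentence makes either text an exception to the other, in the body or in the synopsis.

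**4. What happens on resumption?** The withhold paragraph asks for at least 48 hours on the same antihypertensives and controlled BP, gives no dose, and points below. The text below specifies a restart dose only for BP that persists despite maximal therapy or recurs, and that dose is one level (20%) lower. A further recurrence is referred to the sponsor. The dose on resumption for a subject held at a first reading is therefore not given.

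**5. How would the SAP record it?** Under SAP Section 5.6.1.3, a zero-dose period followed by the same dose is an interruption. A zero-dose period followed by a lower dose is a reduction and not an interruption. The same first reading can therefore produce three records:

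- held, then same dose: interruption;
- held, then lower dose: reduction;
- continued: neither.

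**The case against.** The best reply is that the texts can be read together. The operative condition for withholding is risk of a crisis or of serious complications, and the BP level is only an example beside cardiac risk, intracerebral hemorrhage and other comorbidities. The later guidelines would then be the default and the earlier paragraph an exception for high-risk subjects. That is an ordinary protocol structure, and it may be what was intended. It does not settle the matter, because the example list offers the BP level by itself, with no further condition. Taken literally, a confirmed reading that opens the default pathway already matches the exception.

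Figure 2 is a fair limit on the point. Section 9.4.1.4 says that it shows the hypertension procedures, and the footnotes to Tables 7, 8 and 9 send sites to it. It may put the steps in a clear order. It is not reproduced in the text reviewed, so divergent site behavior is possible from the wording but not demonstrated.

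Three stronger readings may tempt a reader, and the documents do not support them.

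- *That everyone reaching the 99th percentile faces contradictory orders.* The word to continue is addressed only to subjects not on antihypertensives. Section 9.4.1.4 starts such treatment from the 95th percentile [140 systolic or 90 diastolic], so some subjects will already be treated.
- *That the 31% for hypertension in Section 7.1.3.3 sizes the problem.* That is a DLT figure from earlier Phase 1b studies, not a rate of BP at or above the 99th percentile. Section 7.1.3.4 states that there was no prior experience in children, and Section 7.1.3.1 reports an apparently lower incidence of hypertension in pediatric patients for the drug class.
- *That DLT counts, and so the recommended doses, are distorted through the criterion of less than 75% of planned dosage.* If whole doses are missed and dosing is otherwise full, 75% of 28 is 21 doses, so Cohort 1 needs at least 8 missed. 75% of 21 is 15.75 doses, so Cohort 3A needs at least 6 missed (15/21 = 71.4%; 16/21 = 76.2%). A 48-hour hold, about 2 doses, leaves 26/28 = 92.9% or 19/21 = 90.5%. Only a much longer wait for BP control would reach the criterion. Hypertension also has its own BP-based DLT criteria, and SAP Sections 3.4.1 and 3.4.2 report both recommended doses as determined.

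**Conclusion.** The inconsistency is real and narrow. For a previously untreated subject with confirmed BP at or above the 99th percentile, the visible text supports two opposite actions and does not rank them, and the dose on resumption after a hold at a first reading is missing. For subjects already on antihypertensives, the tension is by implication only.

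The consequence is a possible difference between sites in a safety action, and hence in whether an episode enters the SAP tables as an interruption, a reduction or neither. It cannot be expressed as a number of subjects, because the documents give no expected frequency of such readings. No effect on a Phase 2 primary endpoint is shown.

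The conclusion assumes that sites work from the text of Section 9.4.1.4 or the synopsis, and that Figure 2 does not already settle the order. Even if it does, the wording should be made to agree with it. No view is taken here on which action is clinically right.

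**What to change.** Reconcile the withholding paragraph and the guidelines in Section 9.4.1.4 so that:

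- one confirmed reading leads to one action, with the order of precedence stated;
- the action for subjects already on antihypertensives is written out instead of implied;
- a single resumption rule, including the dose, covers every situation in which drug is held for blood pressure.

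Make the same change in the synopsis and bring Figure 2 into line. The choice of action and of resumption dose belongs to the clinical team.

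The cost is a protocol clarification with no added subjects, visits or procedures. The definitions in SAP Section 5.6.1.3 can stay as they are. If data were collected under the present wording, a note to the interruption and reduction tables should say that site practice at this BP level may have differed.

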9.4.1.5 Management of Posterior Reversible Leukoencephalopathy Syndrome (PRES)

A thorough medical history and a comprehensive physical examination, including a neurological examination, should be conducted as detailed in the Schedule of Assessments (Table 7, Table 8, and Table 9) and as clinically indicated.

Any subject with signs or symptoms of headache, confusion, seizure, or visual change combined with hypertension (usually but not always severe) should be immediately evaluated with brain MRI to evaluate the possibility of posterior reversible leukoencephalopathy syndrome (PRES), a Grade 4 hypertension adverse event per CTCAE v4.03. In subjects with suspected PRES, lenvatinib should be immediately withheld, and if the condition is confirmed by MRI, lenvatinib must be permanently discontinued (see

Table 3). Appropriate measures should be taken to control blood pressure (see [Section 9.4.1.4](#)), and neurologic consultation is advised.

9.4.1.6 Management of Proteinuria

Regular assessment for proteinuria should be conducted as detailed in the Schedule of Assessments ([Table 7](#), [Table 8](#), and [Table 9](#)). Guidelines for assessment and management of proteinuria are summarized as follows:

- Initial episode of proteinuria: If proteinuria $\geq 2+$ is detected on urine dipstick testing, study drug will be continued and a spot protein-creatinine ratio test and if possible a 24-hour urine collection for total protein will be obtained as soon as possible within 72 hours to verify the grade of proteinuria. Grading according to CTCAE v4.03 ([Appendix 2](#)) will be based on the protein-creatinine ratio. And wherever possible also on the 24-hour urinary protein result per investigators discretion. Management of lenvatinib administration will be based on the grade of proteinuria according to [Table 3](#).
- During the Treatment Period, urine dipstick testing for subjects with proteinuria $\geq 2+$ should be performed every 2 weeks (on Day 15 or more frequently as clinically indicated) until the results have been 1+ or negative for 3 consecutive months. Any subsequent increases in the level of proteinuria $\geq 2+$ on urine dipstick testing must be confirmed with a spot protein-creatinine ratio test and if possible a 24-hour urinary protein test per investigators discretion which will be assessed and graded and managed according to the dose reduction and interruption instructions provided in the table above. If a new event of proteinuria $\geq 2+$ occurs, the subject must resume the Day 15 urine dipstick testing for evaluation of proteinuria until results are 1+ or negative for 3 consecutive months.

9.4.1.7 Management of Hepatotoxicity

Regular monitoring of liver function tests (alanine transaminase [ALT], aspartate transaminase [AST], bilirubin levels) should be conducted as detailed in the Schedule of Assessments ([Table 7](#), [Table 8](#), and [Table 9](#)) and as clinically indicated. If signs/symptoms indicating liver injury occur, instructions contained in the table for dose reduction and interruptions of the protocol should be followed (see [Table 3](#), for Study Treatment Dose Reduction and Interruption Instructions). Appropriate supportive care should be provided together with close monitoring. If hepatic failure occurs the study drug must be discontinued.

9.4.1.8 Management of Thromboembolic Events

Subjects should be advised to pay attention to symptoms suggestive of venous thromboembolic events which include acute onset of shortness of breath, dyspnea, chest pain, cough, hemoptysis, tachypnea, tachycardia, cyanosis, deep vein thrombosis signs including lower-extremity swelling, redness and warmth to touch or tenderness. In case any of these symptoms appear, subjects should be instructed to report such symptoms promptly to the

treating physician. If a thromboembolic event is confirmed, instructions contained in the table for dose reduction and interruptions of the protocol should be followed, (see [Table 3](#)), for Study Treatment Dose Reduction and Interruption Instructions). Appropriate supportive care should be provided together with close monitoring. If a subject experiences life-threatening (Grade 4) thromboembolic reactions, including pulmonary embolism, the study drug must be discontinued.

9.4.1.9 Management of Hypocalcemia

Serum calcium should be monitored monthly per the Schedule of Assessments. Hypocalcemia should be treated per institutional guidelines (eg, using appropriate calcium, magnesium, and Vitamin D supplementation) until resolution.

9.4.1.10 Management of Gastrointestinal Symptoms and Acute Abdominal Pain

Initial management of acute abdominal pain in these study subjects should be focused on treating the underlying cause where possible, ensuring appropriate hydration/rehydration, and symptomatic pain improvement consistent with subject's age and in accordance to local and institutional standards of care. Appropriate supportive care should be provided together with close monitoring.

For adverse events of abdominal pain believed related to lenvatinib or more specific adverse events believed related to lenvatinib that result in the symptom of abdominal pain, instructions contained in [Table 3](#) regarding study treatment dose reduction and interruption instructions. For Grade 4 adverse events that result in abdominal pain, study drug must be discontinued.

Gastrointestinal (GI) symptoms including diarrhea should be managed by providing symptomatic treatment. If the symptoms persist (eg, diarrhea for more than 10 days), Study Treatment Interruption and Reduction guideline should be followed. Gastrointestinal symptoms should be monitored closely and evaluated using CT, Contrast-Enhanced MRI, ultrasound, or other diagnostic imaging if clinically indicated, at the investigator's discretion. All GI symptoms should be recorded in the diary provided.

9.4.1.11 For additional information please refer to the current Investigator's Brochure (Lenvatinib Investigator's Brochure). Management of Ifosfamide-Etoposide Associated Toxicity

All sites participating in this trial have had considerable experience with these chemotherapeutic agents. Blood counts should be closely monitored during and prior to the next cycle of chemotherapy. Chemotherapy-associated myelosuppression should be managed by G-CSF. It is recommended that pegylated G-CSF or G-CSF be administered at least 24 to 72 hours after completion of ifosfamide-etoposide chemotherapy; use of G-CSF is recommended until WBC counts are $\geq 1 \times 10^9/L$. Guidelines for dose modification for ifosfamide and etoposide associated toxicities are provided in the [Table 4](#) below.

Details of ifosfamide and etoposide dose interruption and reduction as well as management of toxicity can be found in the Summary of Product Characteristics (SmPC), and may be followed as per local and institutional guidelines. The SmPC will be provided to the study sites in the Investigator and Pharmacy files in the relevant local language. For additional information investigators may refer to the SmPC or Euramos-1 protocol ([ISRCTN67613327](#) [EudraCT no. 2004-000242-20](#)).

Table 4 Criteria for Dose Modification of Chemotherapy Dose

Toxicity	Grade	Action
Neutropenia	Grade 4	Monitor ANC counts every 3 days until resolved to < Grade 3
Febrile neutropenia	Grade 4	Reduce the next dose of ifosfamide and etoposide by 20%
Mucositis	Repeated grade 3 or Grade 4	Reduce etoposide by 20%
Renal Toxicity	Serum creatinine is 1.5 – 3 × ULN maximum serum creatinine for age and gender	Interrupt ifosfamide and etoposide for 1 week
Hematuria	>50 RBC/ high power field (hpf)	Interrupt ifosfamide for 1 week
Neurological Toxicity	≥ Grade 2	Interrupt and reduce ifosfamide and etoposide each by 20% of the previous dose. After 2 dose reductions subject must discontinue the chemotherapy drugs, but if benefiting, can continue on single-agent lenvatinib at the investigator's discretion

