- Mucositis (repeated Grade 3 or Grade 4): Reduce etoposide by 20%
- Renal Toxicity: If serum creatinine $> 1.5 - 3 \times \text{ULN}$ - interrupt ifosfamide and etoposide for 1 week
- Hematuria: Interrupt ifosfamide and etoposide if hematuria $> 50 \text{ RBC}/\text{high power field (hpf)}$

- Neurological Toxicity: Interrupt and reduce ifosfamide and etoposide each by 20% of the previous dose. After 2 dose reductions, the subject must discontinue the chemotherapy drugs, but if there is benefit, the subject can continue on single-agent lenvatinib at the investigator's discretion

Details of ifosfamide and etoposide dose interruption and reduction as well as management of toxicity can be found in the Summary of Product Characteristics (SmPC), and should be followed according to local and institutional guidelines. The SmPC will be provided to the study sites in the Investigator and Pharmacy files in the relevant local language. For additional information, investigators may refer to the SmPC or Euramos-1 protocol ([ISRCTN67613327](https://isrctn.com/ISRCTN67613327) EudraCT no. 2004-000242-20).

Duration of Treatment

Subjects benefiting from study treatment in the opinion of the investigator will continue to receive treatment until disease progression, intolerable toxicity, subject noncompliance with safety or efficacy assessments, initiation of another anticancer therapy, voluntary discontinuation by the subject at any time, or study termination by the sponsor, whichever occurs first.

Concomitant Drug/Therapy

Prophylactic use of granulocyte colony-stimulating factors (G-CSFs) is not permitted during this study in Cohorts 1, 2A, and 2B. G-CSF use is recommended for Cohorts 3A and 3B to mitigate the toxicity of ifosfamide and etoposide).

The following concomitant treatments/procedures are allowed:

- a. Removal of existing (not new) osteosarcoma metastatic lesion (surgical, radiofrequency ablation, etc) is allowed only:
 - After completion of the first 4 months of the Treatment Period without progression, and
 - Before the first 4 months of the Treatment Period only if there is disease progression assessed by the investigator and the subject will discontinue the study for progression
- b. Palliative radiotherapy in Cohorts 2 and 3B is allowed for ≤ 2 significantly symptomatic nontarget lesions. For Cohorts 1 and 3A, palliative radiotherapy will be allowed after the RD is determined.

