3.5 Toxicity Management

Toxicity will be managed by treatment interruption, dose reduction and/or treatment discontinuation. Dose reduction and interruption for subjects who experience lenvatinib-related toxicity and ifosfamide/etoposide-associated toxicity will be in accordance with the protocol-specified dose reduction and interruption instructions (Sections 9.4.1.2 and 9.4.1.11 of the Protocol).

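### At the same hematuria threshold the synopsis interrupts ifosfamide and etoposide with no stated duration, while Table 4 interrupts ifosfamide alone for 1 week

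*Protocol*

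**What the plan says.** The protocol lists its guidelines for chemotherapy-related toxicity twice: as bullets in the synopsis, under the management of ifosfamide- and etoposide-associated toxicity, and as Table 4 in Section 9.4.1.11. Both are current text.

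For hematuria, the synopsis bullet starts "Hematuria: Interrupt ifosfamide and etoposide if hematuria", sets the threshold at more than 50 RBC/hpf, and stops there. Table 4, at the same threshold, says "Interrupt ifosfamide for 1 week".

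Both places also refer the reader to the product information (SmPC) for further detail on interruption and reduction. In the synopsis that detail "should be followed according to local and institutional guidelines"; in Section 9.4.1.11 it "may be followed as per local and institutional guidelines".

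SAP Section 3.5 says toxicity will be managed as the protocol specifies and cites "Sections 9.4.1.2 and 9.4.1.11 of the Protocol". It does not mention the synopsis.

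**The concern.** One laboratory finding triggers two different actions. On one reading etoposide stops; on the other it is not mentioned and may continue. The synopsis also leaves out the duration that Table 4 supplies.

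What is at stake is first the clarity of a safety rule for a cytotoxic drug given to children, adolescents and young adults. Protocol Section 11.2 requires strict adherence to the protocol, and a site cannot comply with both instructions when they differ. Second, the etoposide actually given in Cohorts 3A and 3B can depend on which section a site uses.

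**Working it through.** No figure in the plan needs to be reproduced here. The check is a comparison of texts, followed by a look at when the difference could matter.

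**1. The two hematuria entries**

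| | Synopsis | Section 9.4.1.11, Table 4 |
|---|---|---|
| Trigger | >50 RBC/hpf | >50 RBC/hpf |
| Drugs interrupted | ifosfamide and etoposide | ifosfamide |
| Duration | not stated | 1 week |

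The trigger is identical. On the drugs, the two entries contradict each other. On duration, one is specific and the other is silent.

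**2. Is it only a matter of style?** The neighbouring entries say not. For renal toxicity the synopsis has "interrupt ifosfamide and etoposide for 1 week" and Table 4 has "Interrupt ifosfamide and etoposide for 1 week": same drugs, same duration. Febrile neutropenia reduces both drugs by 20% in both places, mucositis reduces etoposide by 20% in both, and neurological toxicity interrupts and reduces both drugs by 20% in both. Each list names etoposide where etoposide is meant, and each can state a duration. A shortened synopsis might drop a duration, but here it names a drug that the fuller table leaves out.

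**3. Does anything settle it?** No statement gives the body precedence over the synopsis. SAP Section 3.5 points to Section 9.4.1.11, but an analysis plan's cross-reference does not correct the protocol synopsis. The SmPC fallback is worded with different force in the two places, so it does not settle the matter either.

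**4. When could the drug difference matter?** Ifosfamide and etoposide are given on Days 1 to 3 of each 21-day cycle, for at most 5 cycles. Suppose hematuria starts on Day d and the hold runs to Day d + 7. The next course is due on Day 22. The hold clears it when d + 7 ≤ 21, that is, d ≤ 14.

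- Onset on Days 4 to 14: a 1-week hold covers no scheduled etoposide day, so holding or not holding etoposide makes no difference.
- Onset on Days 1 to 3: any etoposide days left in the current course are affected.
- Onset on Days 15 to 21: the hold can reach the next course.
- After Day 3 of the fifth course: no etoposide remains to be given.

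Applying 1 week to the synopsis rule is an assumption, since the synopsis gives no period. If a site took it to mean longer, earlier onset days would also matter and ifosfamide could be affected too. The documents give no figure for that.

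**5. Which reported quantity could move?** SAP Section 5.6.1.2 summarizes cumulative dose, dose intensity and percentage of planned dose separately for each drug. Section 5.6.1.1 counts the duration of the IV drugs as days actually given. With constant BSA and k etoposide days given at 100 mg/m², dose intensity is 100k / k = 100 mg/m²/day whatever k is. Missed etoposide days therefore leave dose intensity and the percentage of planned dose unchanged. The quantity that can move is cumulative dose, and only if the days are omitted and not made up later.

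**The case against.** The strongest reply is that little follows from the discrepancy. Both lists are presented as guidelines and leave room for local practice. The synopsis is silent on duration, which is not the same as prescribing an indefinite hold. A difference between sites needs two things together: sites working from different sections, and an event close to a scheduled course. All of that stands, and it is why the consequence is put as possible and not certain. It does not remove the contradiction over which drug is held.

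Three stronger readings are tempting, and the documents do not support them.

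- *A fifth of the etoposide is lost.* Planned etoposide is 100 mg/m² × 3 days × 5 cycles = 1500 mg/m², and one course is 300 mg/m², or 20%. But neither entry says a course is dropped. Both say interrupt, and a course may be delayed or only partly affected. Protocol Section 9.1.2 starts new cycles regardless of interruptions, which makes omission possible, but the protocol does not say it follows.
- *The count of interruptions changes.* SAP Section 5.6.1.3 limits the derivation of dose interruptions to lenvatinib. A chemotherapy hold does not enter that count on either reading.
- *Cohort 3A DLTs are reclassified.* A delay of 7 days or more in the next chemotherapy course is a DLT criterion in Section 9.4.1.1. Ifosfamide is held on both readings, so the course may be delayed on both, and the documents do not establish a case in which only one reading meets the criterion. SAP Section 3.4.2 also records the combination dose as already determined, so rewording would not alter that decision.

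**Conclusion.** The point holds as an internal contradiction. At one hematuria threshold the protocol names two different sets of drugs to interrupt, with a duration in one place and none in the other, and nothing says which governs. It concerns Cohorts 3A and 3B only, and only subjects who cross the threshold while etoposide is still to be given.

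Its statistical reach is small: possible differences in cumulative etoposide dose, with no effect on the hypotheses, sample sizes or planned tests. It deserves correction mainly because a safety instruction should be stated once. The practical consequence assumes that sites do not all read the same section and that some events fall around a course. The documents show neither how sites use the two sections nor how often such hematuria is expected.

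**What to change.** Reconcile the synopsis bullet and the Table 4 hematuria row so that both name the same drug(s) and the same duration. The sponsor decides the content; this review takes no position on which instruction is right. As a minor accompanying edit, use the same verb in both places for how the SmPC detail is to be applied.

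The cost is about one line of protocol text in the synopsis or in Table 4, plus the verb. The SAP needs no change, because Section 3.5 already defers to the protocol.
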